6.2.1 LIST OF METHODS AND PRESENTATION

A table with each feasibility criterion will be reported, alongside the percentage or nominal value for each of the sub-categories.

Means, medians, standard deviations, (empirical) 95% confidence intervals and ranges will be reported for continuous covariates, while for their respective binary transformations, we will report frequencies and percentages.

The impact of each lifestyle factor of interest (namely sleep, diet, physical activity) will be estimated as a causal treatment effect (e.g. ATE or ATT) (Markoulidakis, Taiyari, et al., 2021) using the doubly robust model. PS and balancing weights (assuming the availability of a large enough sample size, and that adequate balance is achieved – this is defined as the maximum KS statistic of all balancing covariates being below or equal to 0.1) will be used to control for confounding bias. The covariates which will be used to control for confounding bias are the lifestyle factors not under study in each case (e.g., when modelling the effect of sleep on the progression of cUHDRS, then diet and physical activity will be considered as confounders), as well as the baseline value of cUHDRS. If sample size allows, additional covariates will be added to control for confounding bias, including age and HD stage. If adequate balance is not achieved at baseline (defined as maximum KS statistic below or equal to 0.1), then mean differences of the outcome will be reported, and/or estimates using a regression model adjusting for the other two lifestyle factors, age, and HD stage. In the latter case, no balancing weights will be used. The full analysis will be re-attempted using the four components of cUHDRS as outcome variables, and similar results as for the original analysis will be reported.

TPL/008/2(v1.0)

DOMINO-HD: STATISTICAL ANALYSIS PLAN

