6.2.2 COVARIATE ADJUSTMENT

Unweighted analyses (using regression models) will control for age, HD stage, as well as baseline values for the outcomes. Additionally, we will control for the two lifestyle (the continuous version of these) factors not included in each case.

The primary goal is to control for confounding bias, using PS and balancing weights (Markoulidakis, Taiyari, et al., 2021), for the two lifestyle factors other than the one under study in each case. Expecting limitations due to the restricted sample size (Markoulidakis, Holmans, et al., 2021), we will attempt to balance additionally for age, HD stage, and baseline values of the outcome.

The outcome analysis will also be performed using the LifeHD score constructed, as a categorical covariate, with and without the use of PS and balancing weights. The LifeHD score will be used both in addition to the individual lifestyle factors (e.g. using LifeHD score as 'treatment', and the three lifestyle factors as confounders), and solely – without taking into consideration the other lifestyle factors.

Outcome will be standardised, so that we report standardised effect sizes. The estimand of interest (e.g. ATE or ATT) will be determined based on whether adequate balance is achieved or not. If we are unable to achieve adequate balance, then unweighted regression and means difference will be reported.

Additionally, significance tests for difference of means of the covariates we wish to control for and the outcome will be reported. The pseudo-groups will be created using the binary indicators of diet, sleep, and physical activity.

Genetic information (via polygenic risk scores) will only be used in the analysis if it is feasible based on the available sample.

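### Sections 6.2.1 and 6.2.2 of the SAP give different covariate lists for the same secondary analysis, and 6.2.1 leaves the baseline outcome out of the unweighted fallback

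*SAP*

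**What the plan says.** Both sections describe the analysis of cUHDRS and its four components, the secondary outcomes of SAP section 6.1.3.

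**Unweighted fallback** (maximum Kolmogorov-Smirnov statistic above 0.1, no weights used):
- Section 6.2.1 says that mean differences "will be reported, and/or estimates using a regression model adjusting for the other two lifestyle factors, age, and HD stage". The baseline outcome is not in the list.
- Section 6.2.2 states: "Unweighted analyses (using regression models) will control for age, HD stage, as well as baseline values for the outcomes". It adds the other two lifestyle factors in continuous form.

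**Weighted analysis:**
- Section 6.2.1 puts the other two lifestyle factors in the core set, "as well as the baseline value of cUHDRS". Age and stage are conditional: "If sample size allows, additional covariates will be added to control for confounding bias, including age and HD stage".
- Section 6.2.2 makes the two lifestyle factors the primary goal. Of the rest it says "we will attempt to balance additionally for age, HD stage, and baseline values of the outcome".

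**Raw differences when balance fails:**
- Section 6.2.1: "then mean differences of the outcome will be reported, and/or estimates using a regression model".
- Section 6.2.2: "If we are unable to achieve adequate balance, then unweighted regression and means difference will be reported". It also plans significance tests for the difference in outcome means between the pseudo-groups. Section 4.1 judges all p-values at 5%, and section 4.1.1 makes no multiplicity adjustment.

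**Outcome:** section 6.1.5 says the secondary outcomes are assessed 12 months after baseline. Sections 6.2 and 6.2.1 speak of progression. Neither says whether the 12-month level or the change from baseline is modelled.

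**The concern.** Two analysts could each follow this SAP and fit different models, and the choice could be made after seeing the results. The disagreement concerns the covariate that matters most. The question is progression, and people with more advanced disease may well move, sleep and eat differently already at baseline. If the 12-month level is compared without its baseline value, part of that existing difference is reported as a lifestyle effect, which section 6.2.1 calls a causal treatment effect.

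HD stage is only a partial substitute. Apart from the late pre-manifest group, it is a banding of TFC, which is one of the four cUHDRS components.

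The fallback is also a plausible route. Section 6.1.1 cites 60-80 observations per covariate per treatment group. A first-tertile split of 300 leaves 100 in the smaller group, which by that rule supports 100/80 = 1.25 to 100/60 = 1.67 covariates. With 450 participants the group is 150, which supports 1.9 to 2.5. The core sets already hold two covariates (6.2.2) or three (6.2.1). If balance fails because of baseline severity, the 6.2.1 fallback drops the adjustment exactly where it is needed.

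**Working it through.** **Step 1. The lists side by side**

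| Analysis | Section 6.2.1 | Section 6.2.2 |
|---|---|---|
| Unweighted regression | other two lifestyle factors, age, stage | the same, plus baseline of the outcome |
| Weights, core set | other two lifestyle factors, baseline cUHDRS | other two lifestyle factors |
| Weights, if feasible | age, stage | age, stage, baseline of the outcome |
| Raw difference | may stand alone | reported with the regression |

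The two conflicts run in opposite directions, so neither section simply completes the other. Section 6.2.1 also names baseline cUHDRS only, although each component is analysed as an outcome in turn.

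**Step 2. The plan's own figure.** The SAP gives no figure on this point. Its only effect size is the detectable 0.23 in section 3.3, for a continuous predictor. Without a weighting penalty, (1.960 + 0.842)/√300 = 0.162. Reaching 0.23 needs a design effect of 300 × (0.23/2.802)² ≈ 2.02, which is not stated. This figure is not used below.

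**Step 3. Illustration for the 12-month level, true lifestyle effect zero.** From the SAP: n = 300, first-tertile split (main cut for sleep), 5% level (two-sided assumed). Assumed, because the documents give no values: baseline to 12-month correlation ρ = 0.9; TFC to baseline cUHDRS 0.8; lifestyle to baseline cUHDRS r = 0.1-0.4; stage as four bands of TFC; the other two lifestyle factors also related to severity.

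*Raw difference, by hand.* A split at the first tertile separates the group means of the exposure by φ(z₁⸝₃)/(1/3 × 2/3) = 0.3636/0.2222 = 1.636 SD. The false effect is 1.636 × r × ρ:
- r = 0.1: 1.636 × 0.1 × 0.9 = 0.15 SD
- r = 0.2: 0.29 SD
- r = 0.3: 0.44 SD
- r = 0.4: 0.59 SD

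*Simulation, with all the covariates that each section lists:*

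| Analysis | False effect, r = 0.1-0.4 | p < 0.05 | At r = 0.3 |
|---|---|---|---|
| Raw difference | 0.14-0.59 SD | 21-100% | 0.44 SD, 96% |
| 6.2.1 regression | 0.04-0.23 SD | 8-71% | 0.12-0.17 SD, 25-48% |
| 6.2.2 regression (baseline added) | about 0.00 SD | about 5% | about 0.00 SD, about 5% |

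The standard error falls from about 0.09 to 0.056 when baseline is added. In the 6.2.1 row at r = 0.3, the lower end applies when the other two lifestyle factors are also moderately correlated with the factor under study.

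*Sensitivity.* The TFC to cUHDRS correlation was varied over 0.70-0.85, with other lifestyle factors that say little about severity. The 6.2.1 regression then gives 0.05-0.32 SD and 9-89% over the same range of r. With 210 analysed (70% of 300) and r = 0.3, it gives 0.15-0.23 SD and 28-49%.

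**Step 4. If change is analysed.** Change = (0.9 - 1) × baseline + residual, with variance 0.01 + 0.19 = 0.20 and SD 0.447. The raw false effect at r = 0.3 is 1.636 × 0.3 × (-0.1)/0.447 = -0.11 SD, with about 15% significant. The 6.2.1 regression gives about -0.05 SD and 7-8%.

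**Step 5. TFC as outcome (12-month level).** Stage already bands baseline TFC. At r = 0.3 the 6.2.1 regression gives about 0.04 SD and 9%.

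**The case against.** Section 6.2.2 is the dedicated section on covariate adjustment. It includes baseline in unweighted regressions and reports the regression together with the mean difference, so the bad result arises only if 6.2.1 is followed instead. That is true, but the SAP gives neither section precedence, and 6.2.1 is where the reported methods are listed.

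A reader might infer that 6.2.2 removes baseline from the weighted analysis. It does not. Attempting to balance baseline concerns the weights, while 6.2.1 specifies a doubly robust model, and nothing takes baseline out of that model's outcome regression. This is a difference in priority, not an exclusion. It still leaves baseline adjustment unguaranteed.

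A reader might also infer that any lifestyle effect reported under this plan would be nothing but baseline severity. The documents do not support that. They give no correlation between lifestyle and severity, the bias is small if change is modelled or TFC is the outcome, and at r = 0.1 the 6.2.1 regression can be as little as 0.04 SD off. The tertile split also does not apply to step counts, which are cut at 5000 per day; for activity it applies to MET-minutes, the alternative measure.

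The planned OVtool plots and E-values (sections 6.2.3 and 6.2.5) would probe confounding, but they do not replace adjustment for a measured baseline.

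Finally, neither list includes site, although there are five sites. The two sections do not contradict each other on this, and nothing in the SAP shows a resulting bias, so it is not part of this point.

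**Conclusion.** The contradiction stands on the text alone: two covariate sets for one fallback regression, two rankings of baseline in the weights, and two rules on whether a raw difference may be the only result.

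Its consequence is conditional. It is material if the 12-month level is analysed and lifestyle correlates with baseline severity at about 0.2 or more, and minor if change is analysed. The simulated sizes rest on assumed correlations and show what could happen, not what will. The direction, with existing severity counted as a lifestyle effect, follows whenever the level is analysed and that correlation is not zero.

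The outcomes concerned are secondary in an exploratory feasibility study, and the feasibility percentages for completeness, linkage and follow-up do not depend on this choice. Severity: should be fixed before analysis.

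**What to change.** Use one covariate list in both sections, for example: every unweighted regression, and the outcome regression of every doubly robust model, includes the baseline value of the outcome being analysed (cUHDRS or the component), the other two lifestyle factors in continuous form, age and HD stage. These terms stay in the outcome regression even where sample size limits what the weights can balance.

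Make this baseline-adjusted regression the inferential fallback. Label raw mean differences of the outcome, and their significance tests, as descriptive, and delete the and/or.

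With baseline entered linearly, modelling the level or the change gives the same lifestyle coefficient before standardisation, so this also removes most of the ambiguity about which is meant.

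The cost is wording only. Table 5 already has cUHDRS and its components measured at baseline and at 12 months, and the regression spends one more degree of freedom than the 6.2.1 list.

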6.2.2 COVARIATE ADJUSTMENT

Unweighted analyses (using regression models) will control for age, HD stage, as well as baseline values for the outcomes. Additionally, we will control for the two lifestyle (the continuous version of these) factors not included in each case.

The primary goal is to control for confounding bias, using PS and balancing weights (Markoulidakis, Taiyari, et al., 2021), for the two lifestyle factors other than the one under study in each case. Expecting limitations due to the restricted sample size (Markoulidakis, Holmans, et al., 2021), we will attempt to balance additionally for age, HD stage, and baseline values of the outcome.

The outcome analysis will also be performed using the LifeHD score constructed, as a categorical covariate, with and without the use of PS and balancing weights. The LifeHD score will be used both in addition to the individual lifestyle factors (e.g. using LifeHD score as 'treatment', and the three lifestyle factors as confounders), and solely – without taking into consideration the other lifestyle factors.

Outcome will be standardised, so that we report standardised effect sizes. The estimand of interest (e.g. ATE or ATT) will be determined based on whether adequate balance is achieved or not. If we are unable to achieve adequate balance, then unweighted regression and means difference will be reported.

Additionally, significance tests for difference of means of the covariates we wish to control for and the outcome will be reported. The pseudo-groups will be created using the binary indicators of diet, sleep, and physical activity.

Genetic information (via polygenic risk scores) will only be used in the analysis if it is feasible based on the available sample.

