3.3 SAMPLE SIZE

Based on previous clinical trials with similar assessments and participant burden (see the protocol for more details), it is estimated that a minimum of 60 participants (and up to 90) per site will be required. This will result in a total of 300-450 participants across the five clinical sites. With a sample size of 300, conservative assumptions about the impact of the propensity score weighting, and a type I error rate of 0.05, we will have 80% power to detect effect sizes that are at least as large as 0.23 for each environmental measure when they are modelled as continuous predictors. This represents the minimum change in the HD composite outcome that would be detected as statistically significant with 80% power for a 1-unit change in the

TPL/008/2(v1.0)

DOMINO-HD: STATISTICAL ANALYSIS PLAN

environmental measure, suggesting the study has reasonable power for small to moderate effects.

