6.1.3 LIST OF SECONDARY OUTCOMES

We will use a clinical composite score for the initial secondary analyses, namely the composite Unified Huntington's Disease Rating Scale (cUHDRS) defined by (Schobel et al., 2017) as follows:

$$cUHDRS = \frac{TFC - 10.4}{1.9} - \frac{TMS - 29.7}{14.9} + \frac{SDMT - 28.4}{11.3} + \frac{SWRT - 66.1}{20.1} + 10$$

where:

- Total Functional Capacity (TFC) is a standard assessment of overall function in HD and ranges from 13 (normal function) to 0 (complete loss of function).
- The Total Motor Score (TMS) has a maximum score of 124. Higher values indicate more severe impairment.
- SDMT is the Symbol Digit Modality Test. Higher scores reflect better cognitive functioning.
- SWRT is the Stroop Word Reading Test. Higher scores reflect better cognitive functioning.

The higher the value of cUHDRS, the better the condition of the patient (lower severity). As the disease progresses and the condition of the individual becomes more severe, the cUHDRS drops.

Individual components of cUDHRS (namely TFC, TMS, SDMT and SWRT) will also explored. This means that the entire analysis described below for the cUHDRS as an outcome will be reproduced for each of the four cUHDRS components (one at a time).

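### Sections 6.2.1 and 6.2.2 of the SAP give three conflicting baseline adjustments, and none commits to baseline TMS when steps are related to SDMT or SWRT

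*SAP*

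**What the plan says.** Three baseline adjustments can be read from the SAP.

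- **6.2.1, weighted analysis.** The confounders are the two lifestyle factors not under study "as well as the baseline value of cUHDRS". Age and HD stage are conditional: "If sample size allows, additional covariates will be added to control for confounding bias, including age and HD stage".
- **6.2.1, fallback when balance fails.** Mean differences and/or a regression on the other two lifestyle factors, age and HD stage. No baseline outcome is listed.
- **6.2.2.** "Unweighted analyses (using regression models) will control for age, HD stage, as well as baseline values for the outcomes", together with the other two lifestyle factors in continuous form. For the weighted analysis the main aim is balance on those two factors, and beyond that "we will attempt to balance additionally for age, HD stage, and baseline values of the outcome".

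On the components, 6.2.1 says "The full analysis will be re-attempted using the four components of cUHDRS as outcome variables", and 6.1.3 says the same of the whole cUHDRS analysis. Neither says whether the baseline covariate becomes the component's own value or stays cUHDRS. Baseline TMS is collected (Table 1, Table 5) but is not named as a covariate for SDMT or SWRT. Section 6.2.1 describes the result as a causal treatment effect. Physical activity is daily steps split at 5000 (section 6.2).

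**The concern.** An analyst fitting the SDMT model could defend baseline SDMT, baseline cUHDRS or no baseline outcome from the text. These are different models, and the choice could be made after the data are seen.

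The second issue is motor severity. Worse motor signs plausibly reduce steps. If they also predict faster cognitive decline at a given starting score, part of an apparent activity effect on SDMT or SWRT is motor severity. HD stage captures little of it: stages 1 to 3 are bands of TFC, and only the late pre-manifest category, defined by absence of motor onset, is motor-based. At stake is whether the cognitive component results can be read as effects of activity.

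**Working it through.** **The plan's own figure.** For N = 300, α = 0.05 and an allowance for weighting, section 3.3 claims: "we will have 80% power to detect effect sizes that are at least as large as 0.23 for each environmental measure". For a standardised slope the detectable effect is (z0.975 + z0.80)/√(N/DE), where DE is the design effect of weighting.
- DE = 1: (1.960 + 0.842)/√300 = 0.162.
- For 0.23: effective N = (2.802/0.23)² ≈ 148, so DE = 300/148.4 ≈ 2.02.

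The weighting assumptions are not given, so 0.23 is compatible with a design effect of about 2 but cannot be reproduced. Nothing below depends on it.

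**Simulation inputs.** From the SAP: the cUHDRS scaling and TFC stage bands. Assumed, because the SAP gives none:
- correlation between component severities, ρ = 0.5 to 0.7;
- correlation of steps with TMS, −0.3 to −0.5;
- direct effect of baseline TMS on 12-month SDMT given baseline SDMT, g = 0 to 0.2 SD;
- 60% classed active;
- late pre-manifest approximated by low motor severity with TFC of at least 11.

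Model (SD units): SDMT at 12 months = 0.85 × baseline SDMT − g × baseline TMS + 0.4 × noise. The true activity effect is zero. Each scenario has 400,000 simulated participants, fitted by linear regression. Weighting and the other two lifestyle factors were not simulated, and SWRT is taken to behave like SDMT.

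**Spurious activity effect on SDMT (SD), with age and HD stage in every model**

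| Baseline covariates | g = 0.05 to 0.20 | g = 0 |
|---|---|---|
| None (6.2.1 fallback) | +0.12 to +0.27 | +0.10 to +0.21 |
| Own baseline (6.2.2) | +0.01 to +0.09 | 0.00 |
| Baseline cUHDRS only (6.2.1) | −0.01 to −0.09 | −0.03 to −0.11 |
| Own baseline + cUHDRS | 0.00 to +0.05 | 0.00 |
| Own baseline + TMS | 0.00 | 0.00 |
| All four components | 0.00 | 0.00 |

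**Hand check of the own-baseline row** (ρ = 0.5, steps–TMS −0.5, g = 0.2, before age and stage).
- Splitting steps at 60% active multiplies correlations by 0.386/√(0.6 × 0.4) = 0.789. So corr(active, TMS) = −0.394 and corr(active, SDMT) = 0.5 × 0.5 × 0.789 = 0.197.
- The slope of −TMS on active, given SDMT, is (0.394 − 0.5 × 0.197)/[(1 − 0.197²) × 0.490] ≈ 0.63.
- Variance of the outcome: 0.7225 + 0.04 + 0.17 + 0.16 = 1.0925, SD 1.045.
- Bias: 0.2 × 0.63/1.045 ≈ 0.12. The simulation gives 0.12 without age and stage, and 0.09 with them. HD stage therefore removes only about a quarter of the bias.

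**At N = 300.** In a separate simulation (3000 replicates, steps split at the median, TMS–SDMT correlation −0.6), own baseline plus HD stage left 0.012 to 0.080 SD, with standard error about 0.05. The nominal 5% test rejected in 5.4% to 36%. With baseline TMS added it rejected in 4.6% to 4.8%.

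**The case against.** The strongest reply is that the text is loose, not exclusive. Read cumulatively, 6.2.1 supplies baseline cUHDRS and 6.2.2 the component's own baseline. The plural in 6.2.2 could cover several baselines, and the list of extra covariates in 6.2.1 is open. This stands as far as it goes. A reader might infer that a component model never holds both baselines, and the SAP does not say that. But it does not commit to both either, and the cumulative reading cannot rescue a fallback that lists no baseline outcome.

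A reader might also infer that motor severity is uncontrolled. That is too strong: late pre-manifest status carries motor information, and TMS is one of the four terms of cUHDRS. Control is partial. Nor does every reading produce a false benefit of activity. With baseline cUHDRS only, the bias runs the other way, because baseline SDMT is not held fixed.

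The sizes are assumption-driven, and this stands. With no direct effect of baseline TMS on later SDMT, the own-baseline bias is zero. The 36% rejection rate needs the extreme values of two inputs and a residual SD of 0.4. In the middle scenario (g = 0.10, steps–TMS −0.5), raising that SD to 0.6–0.8 cuts rejection from about 13% to 7–8%.

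It is also tempting to say that the fallback bias reaches the detectable effect of 0.23. The scales differ: 0.23 is a slope for a continuous predictor, while 0.27 is a difference between two groups. Per SD of the binary indicator it is 0.27 × √(0.6 × 0.4) ≈ 0.13.

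Finally, the SAP keeps covariates few for sample-size reasons, plans OVtool or E-values for omitted confounders, and treats these outcomes as exploratory secondaries. The first limits balancing covariates far more than regression terms. The second probes sensitivity but does not adjust for a covariate already measured. The third limits the severity.

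**Conclusion.** The inconsistency is in the text and needs no assumption: the two sections give three baseline adjustments, the fallback in 6.2.1 disagrees with 6.2.2, and the carry-over to the components is undefined. The incomplete control of motor severity in the cognitive models follows, but its size depends on assumed correlations.

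The fallback with no baseline outcome is the largest problem, biased even when TMS has no direct effect. The own-baseline and cUHDRS-only readings err in opposite directions, so choosing between them could move a null activity effect by roughly 0.04 to 0.13 SD. Entering own baseline plus cUHDRS only about halves the residual bias. Naming TMS, or all four components, removes it here, in a model with no unmeasured confounder.

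Severity is moderate. The change should be made because it is cheap and the estimates are presented as causal, but the primary feasibility outcomes are unaffected.

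**What to change.** 1. State one baseline adjustment set, in the same words, in 6.2.1 and 6.2.2, and say that it applies to each component.
2. In the outcome regression of the doubly robust model and in the fallback regression, adjust every component model for baseline TFC, TMS, SDMT and SWRT. The minimum for SDMT and SWRT is the test's own baseline plus baseline TMS. Baseline cUHDRS is an exact linear combination of the four, so it must not be entered beside them.
3. Add the baseline outcome to the 6.2.1 fallback, for cUHDRS and for each component, so that it agrees with 6.2.2.
4. State which baseline value, cUHDRS or the component's own, is used for balancing in the component analyses. The balancing set need not grow.

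The cost is SAP wording and up to three degrees of freedom beyond the own baseline that 6.2.2 already includes. The values are already collected.

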6. ANALYSIS

6.1 OUTCOME DEFINITIONS

6.1.1 PRIMARY OUTCOME(S)

The primary objective of this study is to establish the feasibility of linking lifestyle, clinical and genetic data and to explore their interplay with HD symptoms and severity.

We will explore the proportions of recruited participants with linked DOMINO-HD and Enroll-HD clinical data as well as linked GWAS data. We will also explore follow-up rates and lifestyle and wearable activity tracker data completeness and balance statistics in important variables. Our data will be used to provide progression criteria recommendations for future studies in this field.

Aspects of feasibility which will be assessed are:

- Completeness of key lifestyle questionnaires (at baseline: HD Pro-Triad, FFQ, LTPA, Sleep, IPAQ, Relationship) data [>80% returned with >80% completeness = feasible, >60% returned with >60% completeness = changes required, <60% returned or <60% completeness = not feasible]
- Completeness of activity tracker data [>70% feasible, 50-70% changes required, <50% not feasible]
- % participants linked with Enroll-HD clinical data [>80% feasible, 60-80% changes required, <60% not feasible]
- % participants linked with GWAS data [>60% feasible, 40-60% changes required, <40% not feasible]
- % participants with follow-up at 12m [>70% feasible, 50-70% changes required, <50% not feasible]
- Feasibility of balancing important covariates. Adequate balance of baseline covariates is achieved when the maximum Kolmogorov-Smirnov (KS) value is equal to or below 0.1. However, as the recommendation is for 60-80 observations per covariate per treatment

TPL/008/2(v1.0)

Centre for Trials Research Canolfan

Ymchwil Treialon

DOMINO-HD: STATISTICAL ANALYSIS PLAN

group (Markoulidakis, Holmans, et al., 2021), the feasibility of achieving balance should be determined alongside the available sample size.

• Agreement between questionnaire and activity tracker data

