Appendix C: LifeHD score

Table 4 reports the covariates which will be included in the LifeHD index. The following algorithm describes the development of the score.

- Step 1. The risk factors will first be included separately in a regression model (together with non-lifestyle factors: age, sex, HD stage, time since diagnosis, and follow-up time since last visit). We will use a linear or logistic regression model, depending on the outcome (continuous or binary). This will also enable us to understand the impact of each category on the outcome variable and define the reference category for each factor. For diet, the sign and magnitude of each category will allow us to understand the most and least beneficial clusters thus the beneficial category is group 1, and the other category is 0. The least beneficial cluster will be the reference category to another (group 1 or higher for more than two categories) will increase the index thus, higher values of the index indicate "better" lifestyle.
- Step 2. Factors that were significant in the first step will be simultaneously placed into a single regression model linear or logistic regression depending on the outcome. (For DOMINO-HD, as the outcome is cUHDRS or its components linear regression will be used.)
- Step 3. From the final regression models of step 2, risk scores will be assigned for each factor with the respective β coefficients (steps 4 and 5).
- Step 4. All β coefficients will be standardised so that the lowest one has a value of 1 this is achieved by multiplying every β coefficient with 1/minimum(β).

TPL/008/2(v1.0)

DOMINO-HD: STATISTICAL ANALYSIS PLAN

Step 4b.	(optional) Rounding each coefficient to the closest integer. In this case,
	all individual scores are positive integers. This will enable easier
	calculaiton of the scores, and higher values of the score would indicate
	better "lifestyle".

Step 5. The risk score for an individual will be obtained by summing the scores for the appropriate level of each of the risk factors.

Correlation and association of LifeHD with the outcome and the lifestyle factors under study (diet, sleep, physical activity) will be tabulated.

Variable	Calibration
Diet*	MDI: 0-5; 6-9
	HEI: 0-59; 60-100
Sleep*	SE > tertile/quantile
	$SE \leq tertile/quantile$
Physical activity*	MET > tertile
	$MET \leq tertile$
BMI*	$BMI \le 25 \text{ normal}$
	$25 < BMI \le 30$ overweight
	BMI > 30 obese
Age**	< 47 years old
	47 – 53 years old
	\geq 53 years old

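### LifeHD is analysed as categorical, but Appendix C yields an ordered numeric sum with no cut-points and anywhere from about 5 to over 200 levels

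*SAP*

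**What the plan says.** Section 6.2.2 gives the coding: "The outcome analysis will also be performed using the LifeHD score constructed, as a categorical covariate". This is to be done with and without propensity score and balancing weights. The same paragraph gives an example of the weighted use: "using LifeHD score as 'treatment', and the three lifestyle factors as confounders".

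Appendix C gives the construction. In Step 2, "Factors that were significant in the first step will be simultaneously placed into a single regression model". Steps 3 and 4 turn the coefficients of that model into points by dividing each by the smallest. Step 4b, marked optional, is "Rounding each coefficient to the closest integer". In Step 5, "The risk score for an individual will be obtained by summing the scores for the appropriate level of each of the risk factors". Appendix C and Table 5 both read a higher score as a better lifestyle.

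No section gives LifeHD a number of categories or a cut-point, and its score range in Table 5 is blank. The other exposures do have a grouping rule: tertiles for sleep and MET-minutes, 5000 steps per day, MDI 6-9, and HEI above 59.

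On the sample needed for weighting, section 6.1.1 says "the recommendation is for 60-80 observations per covariate per treatment" group, to be judged alongside the sample available.

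**The concern.** A categorical analysis needs a known, modest number of groups. Here the groups are whatever distinct sums the algorithm produces, and that number is set by three things left open: how many factors pass the screen, how far apart the coefficients lie, and whether Step 4b is used. The first two come from regressions on the outcome itself, and nothing stops the third being decided after those results are known. The plan therefore does not fix what will be fitted.

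The coding also suits the score poorly. LifeHD is a sum of coefficients from a linear model, so before rounding it is an ordered quantity for which one slope is the natural summary. Treating its values as unordered categories spends one parameter per value and discards the ordering that Appendix C gives it.

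**Working it through.** **Plan's own figures.** The SAP states no number of LifeHD levels, so there is nothing to reproduce on that point. Its power statement in section 3.3 (80% power for 0.23 at N=300) is for environmental measures modelled as continuous predictors. It is consistent with an unstated design effect of about 2: (1.960 + 0.842)/√(300/2.02) = 0.23. No power is stated for a categorical LifeHD.

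**Step 1: possible patterns.** The levels in Table 4 are diet 2, sleep 2, physical activity 2, BMI 3, age 3, CAG 2, HD stage 4 and antidepressant use 2. Antidepressant use is not in the section 6.2 list.
- Seven factors: 2×2×2×3×3×2×4 = 576.
- Eight factors: 576×2 = 1152.
- A few patterns cannot occur. Late pre-manifest requires CAP > 80, and with CAG 41 that means age > 80×6.49/11 = 47.2. Late pre-manifest with CAG below 42 and age under 47 is therefore empty. This removes 2×2×2×3 = 24 of the 576, leaving 552, which changes little.

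**Step 2: occupied values if all patterns were equally likely and every sum distinct.** The expected number is K[1 − (1 − 1/K)^N]. At N=300 this gives 234 (K=576) and 264 (K=1152). At N=450 it gives 313 and 373.

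**Step 3: simulation of Appendix C, Steps 3-5.** All inputs here are assumptions.
- Factors are independent, with level frequencies: diet 0.65/0.35; sleep and activity 1/3, 2/3; BMI 0.55/0.30/0.15; age 0.40/0.25/0.35; CAG 0.30/0.70; stage 0.25/0.40/0.25/0.10; antidepressant 0.5/0.5.
- Coefficients are positive and spread over a 3-fold or 6-fold range.
- There were 300 cohorts per setting. The table gives averages at N=300; paired values are for the 3-fold and 6-fold spread.

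| Factors retained | Patterns | Unrounded: levels (one-person levels; median size) | Rounded: levels | Rounded: median size | Rounded: largest | Rounded: levels with <10 |
|---|---|---|---|---|---|---|
| 8 | 1152 | 232 (182; 1) | 14, 20 | 20, 14 | 53, 37 | 4.6, 8.2 |
| 7 | 576 | 191 (126; 1) | 12, 18 | 23, 16 | 58, 42 | 3.7, 6.9 |
| 5 (sleep, activity, age, CAG, stage) | 96 | 79 (20; 3) | 9, 14 | 32, 21 | 69, 51 | 2.2, 4.2 |
| 4 (diet, sleep, activity, BMI) | 24 | 24 (1; 9) | 7, 10 | 42, 29 | 86, 74 | 0.8, 1.6 |
| 3 (activity, age, stage) | 24 | 24 (0; 11) | 6, 9 | 49, 33 | 91, 72 | 0.8, 1.5 |
| 2 (activity, stage) | 8 | 8 (0; 33) | 4, 5 | 74, 54 | 129, 117 | 0, 0.1 |

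At N=450 with seven or eight factors, the unrounded score takes about 245 and 314 values. The rounded score takes about 12 to 20, of which about 3 to 7 have fewer than 10 people.

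**Step 4: the plan's weighting guide.** With three lifestyle confounders, each group needs 3×60 = 180 to 3×80 = 240. Two groups need 360 to 480. N=300 does not reach two groups, and N=450 reaches two only at the lower figure. Even for a single covariate (60-80 per group), the largest rounded level with seven or eight factors averages only 37 to 58 at N=300.

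**The case against.** A reader might infer that LifeHD always takes about as many values as there are participants, so that its effects cannot be estimated at all. The documents do not support that.
- Every input is already categorised, Step 2 drops non-significant factors, and Step 4b can round. With two or three factors there are at most 24 values, and roughly 4 to 9 after rounding.
- Even unrounded with all factors kept, 191 to 264 values is 64% to 88% of 300. This is an upper-end case, not a property of the score.
- A regression with 12 to 20 levels and 300 participants can be fitted.
- The eighth factor is itself uncertain, since only Table 4 lists it.

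The plan also has a fallback. Section 6.2.1 makes weighting conditional on sample size and balance, and section 6.2.2 reports unweighted regression and mean differences when balance fails. The 60-80 guide is to be read with the available sample, and groups formed by tertiles would miss it too. Categorical coding avoids assuming linearity. LifeHD is an exploratory addition in a feasibility study.

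All of this stands, and it limits the claim. It does not settle the point, because the unweighted fallback also needs defined categories and the plan gives none. The coding works tolerably only if few factors survive or the score is rounded, and neither is fixed in advance.

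**Conclusion.** The point holds in this form: section 6.2.2 prescribes a categorical and weighted analysis of a score that Appendix C leaves numeric, ordered and without cut-points. At N=300 the number of levels could run from about 5 to over 200. At the upper end (unrounded, seven or eight factors) about two thirds to three quarters of levels hold one person (126 of 191; 182 of 232). Effects and weights for such levels are not estimable. After rounding with those factors, an unweighted fit is possible but sparse and ignores the ordering, and weighting is far below the plan's own guide.

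The pattern counts and the 180-240 requirement follow from the SAP. The numbers of occupied levels rest on the assumed frequencies, independence, positive coefficients and their spread. They also take every recruited participant as analysable; losses would thin the levels further. The change should be made, but it concerns an exploratory analysis and leaves the feasibility outcomes untouched.

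**What to change.** In section 6.2.2:
- Make the main LifeHD analysis continuous, reported per SD or per point of the score.
- State the continuous-treatment weighting there. Section 6.2, under sleep, mentions such weighting as a possibility and refers to 6.2.2 for its description, but 6.2.2 contains none.
- Use tertiles (100 per group at N=300) only for unweighted display and to check linearity. They do not meet 180-240 per group, so they should not carry a weighted analysis.

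In Appendix C, fix before outcome data are seen whether Step 4b rounding applies. If a categorical analysis is kept, fix the number of categories and the cut-points at the same time.

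The cost is SAP wording. The small downside is an assumed linear effect, which the tertile display can check. One problem remains: diet, sleep and physical activity are components of LifeHD, so using them as its confounders restricts overlap however the score is coded. That needs separate attention.
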